#### F4 Safety and Adverse Events

Patients will be screened at each office visit. In addition, they will be encouraged to report any concerns or issues to [name] at the contact information listed on the consent form.

#### 4.a Definitions of Adverse Events

Reported adverse events with low-dose naltrexone are rare and mild. Vivid dreams, nightmares, and headaches have been reported with low-dose naltrexone used for other conditions. A recent case series of four patients with lichen planopilaris and a subtype, frontal fibrosing alopecia, treated with oral low-dose naltrexone at 3mg daily showed

reduction of itch, clinical evidence of inflammation of the scalp, and of disease progression. There were no reported adverse events.

#### 4.b Data Collection Procedures for Adverse Events

All adverse events will be recorded in the patient's medical record as well as on a secure document (Excel spreadsheet in Wustl Box) and will be reviewed monthly by the study team.

#### 4.c Reporting Procedures

Subjects may report in person or by telephone at any time during the study.

#### 4.d Adverse Event Reporting Period

September 1st 2019 and December 31st, 2020

#### 4.e Post-study Adverse Event

Patients may report post-study adverse to [name] at any time after the study is completed.

# G Statistical Plan

Longitudinal data from time points at 0,3,6 and 12 months will be analyzed for each component of the data collection form, including components of the patient assessment of itch and burning/pain (each on a 0-10 point scale), physician assessment for erythema and scale (each on a 0-3 scale) as well as longitudinal comparisons of measurement of the scalp involvement (distance in cm from the glabella to hairline in FFA, and area of scarring/redness/scaling in cm2 for LPP). See below for data collection form.

We predict that oral low-dose naltrexone would lead to approximately 2-3 point decrease in each of the 0-10 point patient assessments (itch and burning/pain) and a 1-2 point decrease in each of the 0-3 point physician assessments (erythema and scale). We expect the areas of scalp involvement to remain stable over the analysis period.

Patient characteristics will be summarized using descriptive statistics. The longitudinal outcomes will be analyzed using mixed model analysis to account for the correlation of measures from the same subject. Time effect will be assessed and contrasts will be used to compare mean difference between any two time points of interest. All statistical tests will be two-sided with a significance level of 0.05 and performed with SAS 9.4. Careful attention will be paid to ensuring that data satisfy assumptions required of a particular analytic strategy. When required assumptions are violated, we will explore the use of data transformations and potentially, perform some analyses using non-parametric or semi-parametric methods based on the rank of some variables.

Data on the quantitative effect size of naltrexone for LPP/FFA is limited, but based on clinical experience and descriptive case studies, we would expect patients to start at a 4-5/10 on the itch/pain/burning scales, and predict that it could decrease to 1-2/10 with

naltrexone treatment. Similarly, we expect that patients would start at a 1-2/3 on the physician assessments (erythema and scale) and predict that the physician assessments of erythema and scale could decrease to a 0-1/3. Finally, we expect the areas of scalp involvement to remain stable over the analysis period. Based on existing data showing low number of mild side effects and no serious adverse events, we plan to enroll 75-100 patients, which is the maximum number that we would expect to see over the study period given the low prevalence of disease.

With estimated standard deviation using a rule of thumb based on range of the scales, the anticipated 75-100 patients can achieve at least 80% power to detect mean difference of 0.7-0.8 based on patient assessment as well as 0.21-0.25 based on physician assessment. Therefore, the anticipated sample size is sufficient to detect the expected effects. The power was based on two-sided paired t-test comparing before and after treatment at significance level 0.05.

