## A Introduction

#### A1 Study Abstract

Oral naltrexone was initially FDA approved to treat opioid use disorder and alcohol dependence at doses from 50-100mg/day. At lower doses of 1-5mg/day, naltrexone has been used off-label with success in treatment of several dermatologic conditions including the scarring alopecia (irreversible hair loss), lichen planopilaris. A recent case series of four patients with lichen planopilaris and a subtype, frontal fibrosing alopecia, treated with oral low-dose naltrexone at 3mg daily showed reduction of itch, clinical evidence of inflammation of the scalp, and of disease progression. There were no reported adverse events.

Based on the promising evidence, we propose using low-dose naltrexone at a daily dose of 3mg to treat lichen planopilaris and frontal fibrosing alopecia. The patients would be continued on their other medications for these conditions. The study would be openlabel, so all participants would receive the low-dose naltrexone. Patients would be seen at monthly intervals over a period of six months to monitor their progress.

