### A2 Primary Hypothesis

Does daily oral low-dose naltrexone (3mg per day) reduce symptoms and disease progression in patients with lichen planopilaris and frontal fibrosing alopecia?

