#### Background

Lichen planopilaris (LPP) is an inflammatory, cicatricial alopecia, of which frontal fibrosing alopecia is considered a clinical variant. Clinical features of LPP include perifollicular erythema and scaling leading to destruction of follicular ostia and patchy scarring alopecia. In the frontal fibrosing alopecia variant, hair loss occurs on the frontotermporal region, often with associated eyebrow loss. Symptoms include pruritus, burning, pain, and tenderness. Treatment options are limited and yield inconsistent results. High potency topical steroids and topical tacrolimus are recommended as first line therapies for primary cicatricial alopecias. However, topical corticosteroids may be less effective in FFA. Other frequently utilized treatments include intralesional triamcinolone acetonide and topical minoxidil. Hydroxychloroquine and doxycycline are often used as systemic treatments in both LPP and FFA, whereas finasteride/dutasteride have been reported successfully in FFA. Overall, the level of evidence for the above treatments is limited to level IV or V evidence, and further studies into this scarring disease are needed.

Oral naltrexone is FDA approved to treat opioid dependence and alcohol use disorder at doses from 50-100mg/day. At lower doses of 1-5mg/day, naltrexone has been used off-label with success in treatment of several dermatologic conditions including lichen planopilaris. A recent case series of four patients with lichen planopilaris and a subtype, frontal fibrosing alopecia, treated with oral low-dose naltrexone at 3mg daily showed reduction of pruritus, clinical evidence of scalp inflammation, and of disease progression.

While initial studies using LDN for dermatologic conditions is promising, the level of evidence is low, generally limited to case reports and series. Recently, three excellent summaries of evidence for naltrexone in dermatologic conditions have been published. A recent review article of therapy for FFA includes naltrexone at 3 mg/day in their FFA treatment algorithm.

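### The LPP extent outcome combines irreversible scar with reversible redness and scaling, so a stable area cannot by itself show that scarring slowed or halted

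*Combined protocol and SAP*

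**What the plan says.** Section A2 asks whether naltrexone can "reduce symptoms and disease progression in patients with lichen planopilaris and frontal fibrosing alopecia", so progression is part of the primary hypothesis. Section C1 repeats it more cautiously, as a possible slowing or halting.

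Section G names one extent measure for each disease. For frontal fibrosing alopecia (FFA) it is the "distance in cm from the glabella to hairline in FFA". For LPP it is the "area of scarring/redness/scaling in cm2 for LPP". The plan's prediction for both is: "We expect the areas of scalp involvement to remain stable over the analysis period". It gives no margin or definition of stable.

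The other outcomes in section G are itch and burning/pain (0-10 each) and physician scores for erythema and scale (0-3 each). The physician scores are predicted to fall by 1-2 points.

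The introduction and background describe the disease process. Section A1 speaks of the "scarring alopecia (irreversible hair loss), lichen planopilaris". Section B1 states: "Clinical features of LPP include perifollicular erythema and scaling leading to destruction of follicular ostia and patchy scarring alopecia".

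Section G refers to a data collection form, and section L1 lists a data collection sheet as an attachment. The form itself is not in the text reviewed.

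**The concern.** The parts of the LPP area are expected to move differently. Redness and scaling can clear, and the plan predicts that their scores will fall. Scar, on the protocol's own description, can only hold or grow. Skin that passes from red or scaly to scarred stays inside the measured area, so permanent loss at that site registers as no change. Skin that only loses its redness leaves the area, although the scar is the same size as before.

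The result the plan predicts for LPP, a stable area, therefore has at least two readings: scarring has stopped, or new scar has taken the place of cleared inflammation. The other outcomes named in section G cover symptoms and inflammation severity, so the LPP part of the progression question rests on this area. If scar is not recorded separately at the visit, no later analysis can recover it from the combined figure.

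**Working it through.** **The plan's own figures.** Section G gives no standard deviation, expected change in cm2 or power for the area outcome. Its detectable differences concern the scores only. They reproduce with a two-sided paired t-test at 0.05, 80% power and SD = range/4 (my reading of its rule of thumb):

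- Patient scales, SD 10/4 = 2.5: 0.82 at n = 75 and 0.71 at n = 100 (plan: 0.7-0.8).
- Physician scales, SD 3/4 = 0.75: 0.246 at n = 75 and 0.212 at n = 100 (plan: 0.21-0.25).

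These figures say nothing about extent. The check below is arithmetic on the outcome definition.

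**Illustration with assumed sizes.** The documents give no lesion sizes. Assume a round scar of 20 cm2 with a 0.5 cm red or scaly rim.

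- Scar radius: r = √(20/π) = 2.523 cm.
- Baseline combined area: π × (2.523 + 0.5)² = π × 3.023² = 28.7 cm2.
- Half the rim width scarred: π × (2.523 + 0.25)² = π × 2.773² = 24.2 cm2.
- One further 0.5 cm outward: π × (2.523 + 1.0)² = π × 3.523² = 39.0 cm2.

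| Follow-up state | Scar (cm2) | Change in scar | Combined (cm2) | Change in combined |
|---|---|---|---|---|
| Whole rim scars, redness clears | 28.7 | +44% | 28.7 | 0% |
| Half the rim width scars, redness clears | 24.2 | +21% | 24.2 | −16% |
| Rim clears, no new scar | 20 | 0% | 20 | −30% |
| Whole rim scars, new 0.5 cm rim forms outside | 28.7 | +44% | 39.0 | +36% |
| Rim widens to 1.0 cm, no new scar | 20 | 0% | 39.0 | +36% |

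The changes are 28.7/20 = 1.44, 24.2/20 = 1.21, 24.2/28.7 = 0.84, 20/28.7 = 0.70 and 39.0/28.7 = 1.36.

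In the first two rows scar growth is hidden. The last two rows give the same combined area for 44% scar growth and for none. The combined figure thus fails to identify scar change in either direction.

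**Range.** Let s be the scarred share of the baseline area, and c the share of the inflamed, non-scarred part that no longer counts as inflamed. The total is unchanged if scar gains c(1 − s) of the baseline area. Relative to baseline scar, the hidden growth is c(1 − s)/s.

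| s | c = 0.25 | c = 0.5 | c = 1.0 |
|---|---|---|---|
| 0.5 | 25.0% | 50.0% | 100.0% |
| 0.7 | 10.7% | 21.4% | 42.9% |
| 0.9 | 2.8% | 5.6% | 11.1% |

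The rim example agrees with this formula: s = 20/28.7 = 0.70 and c = 1 give about 43-44%.

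**Can the other outcomes repair it?** The erythema and scale scores are 0-3 grades, not areas, and cannot be subtracted from cm2. The FFA distance does not include redness or scale, so this ambiguity is specific to LPP.

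**The case against.** The strongest objection is that the form is unseen. Section G says that each component of the form will be analysed, and the form may have separate fields for scarring, redness and scaling. The slash does not settle it: section G uses it within one item (burning/pain) and also to list items scored separately (itch/pain/burning). This stands, and the fix is conditional for that reason. It does not remove the point, because section G nowhere says that scarred area is the quantity that will represent LPP progression.

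A reader might infer that the LPP result is biased towards benefit whatever test is used. The documents do not support that. Masking needs inflamed skin outside the scar, clearing of that inflammation, and no new inflamed margin further out. If inflammation lies wholly within the scarred outline, clearing leaves the outline unchanged. If the active margin moves outward or redness flares, the combined area grows and counts against the drug. The plan does not say which pattern to expect. A predicted fall in severity score is also not a predicted fall in inflamed area.

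A reader might also infer that redness and scale are counted twice. They are not: the scores grade severity, the area grades extent, and the plan defines no summed score.

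The issue is also limited in reach. It affects LPP patients only, the stated power concerns only the symptom and physician scores, and the study is uncontrolled, so even a pure scar area could not show that the drug caused any slowing. All of this is true. It bears on the weight of the point, not on whether the combined area measures scarring.

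**Conclusion.** The point holds as a limit on interpretation. With the outcome as section G words it, a stable or smaller combined area in LPP is compatible with growing scar wherever inflamed skin lies outside the scar, so by itself it cannot support a conclusion of slowed or halted progression.

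How far this happens in the trial, and in which direction, cannot be known from the documents. The illustrative sizes (0% combined change with 44% scar growth, and about 3% to 100% hidden growth for s = 0.5-0.9 and c = 0.25-1.0) rest on assumed geometry and proportions. They show what is possible, not what is likely.

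The change is worth making because it is cheap and because the information cannot be recovered after the visits.

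**What to change.** - **Data collection form.** For LPP patients at each visit, record scarred (hair-loss) area and redness/scaling area in cm2 separately, if the form does not already do so.
- **Section G.** State that scarred area is the LPP progression outcome and that redness/scaling area is an inflammation outcome.

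The cost is more than a form field: a second boundary has to be traced and recorded per LPP patient per visit, and assessors need a common rule for tracing it. The visits at 0, 3, 6 and 12 months, the treatment and the planned 75-100 patients are unchanged.

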## C Study Objectives

## C1 Primary Aim

Based on case reports, we expect the participant to benefit though decrease in their symptoms (burning, itching) as well as decreased redness and scale and possibly slowing or halting disease progression.

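### Section G tests at least six outcomes, each at two-sided 0.05, with no primary visit, no multiplicity control and no rule for combining the results into one answer

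*Combined protocol and SAP*

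**What the plan says.** Section G sets the scope: "Longitudinal data from time points at 0,3,6 and 12 months will be analyzed for each component of the data collection form". The outcomes it lists are itch and burning/pain (0-10 each), erythema and scale (0-3 each), glabella-to-hairline distance for frontal fibrosing alopecia, and affected area for lichen planopilaris. The wording makes these six a minimum.

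The analysis is a mixed model for each outcome. On comparisons: "Time effect will be assessed and contrasts will be used to compare mean difference between any two time points of interest". On the error rate: "All statistical tests will be two-sided with a significance level of 0.05 and performed with SAS 9.4". The time points of interest are not listed, and the plan does not say whether contrasts depend on a significant time effect.

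Section G predicts falls of 2-3 points on each 0-10 scale and 1-2 points on each 0-3 scale. For the scalp measures it says: "We expect the areas of scalp involvement to remain stable over the analysis period".

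The sections headed as primary name domains, not a measure or a visit. A2 asks whether treatment will "reduce symptoms and disease progression in patients with lichen planopilaris and frontal fibrosing alopecia". C1 expects a "decrease in their symptoms (burning, itching) as well as decreased redness and scale and possibly slowing or halting disease progression". C2, on the choice of outcome measures, ranks none. The power statement does not say which visit is the after-treatment one: "The power was based on two-sided paired t-test comparing before and after treatment at significance level 0.05".

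**The concern.** The 0.05 level protects each test separately. The A2 question will be answered from several tests together, and the plan does not say how. A reader of the results could not tell whether support required a fall on every scale, on any scale, or at which month. If the choice is made after the data are seen, the chance of a false claim of improvement depends on that choice and can be several times that of a single test. The study is open-label and uncontrolled and its scales are partly subjective, so it has few other safeguards against selective emphasis.

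**Working it through.** **1. The plan's own figure.** Inputs from Section G: n = 75-100, two-sided paired t-test, alpha 0.05, 80% power, SD from a rule of thumb on the range. No SD is printed. I assume range/4 as the SD of the paired difference: 10/4 = 2.5 and 3/4 = 0.75.

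Normal approximation: (1.960 + 0.842) × SD/√n. For n = 75 and SD 2.5 this is 2.802 × 2.5/8.660 = 0.81. The noncentral t gives:

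| Scale | n = 75 | n = 100 | Plan |
|---|---|---|---|
| 0-10 | 0.819 | 0.707 | 0.7-0.8 |
| 0-3 | 0.246 | 0.212 | 0.21-0.25 |

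The figures reproduce within rounding. Range/5 and range/6 do not reproduce them.

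**2. Number of tests.** Four visits give 6 pairwise contrasts per outcome, 3 of them against month 0. The four symptom and sign scales therefore give 4 tests at one follow-up visit, or 4 × 3 = 12 against month 0.

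**3. Chance of at least one false improvement on the four scales when nothing changes.** A single two-sided 0.05 test gives 2.5% in the direction of improvement. With four independent tests at one visit, 1 − 0.975⁴ = 9.6%.

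The documents give no correlations, so between-outcome correlation was varied from 0 to 0.9 in a large-sample normal simulation (200,000 runs per setting, constant within-patient correlation, no dropout). Improvement means a significantly lower value at the later visit. Gated means that a contrast counts only if that scale's overall time test is significant.

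| Rule for support | 0 | 0.3 | 0.5 | 0.7 | 0.9 |
|---|---|---|---|---|---|
| Any scale, month 12 v 0, ungated | 9.6% | 8.6% | 7.7% | 6.5% | 4.7% |
| Any scale, all 12 month-0 contrasts, ungated | 22.8% | 20.3% | 18.1% | 15.3% | 11.3% |
| Any scale, all month-0 contrasts, gated | 7.7% | 7.2% | 6.7% | 5.6% | 4.1% |
| Any scale, month 12 v 0 only, gated | 3.7% | 3.4% | 3.2% | 2.7% | 2.0% |

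If all four scales must fall significantly at one visit, the rate is 0.025⁴, effectively 0%, at correlation 0. By simulation (400,000 runs) it is 0.3% at 0.7 and 0.9% at 0.9.

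A smaller t-based simulation (n = 75 and 100, paired t-tests, Hotelling T² as the time test, 4,000 runs per setting) gave similar rates. Month 12 is used only as an example of a single follow-up visit.

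**4. Detectable differences under Holm over four scales.** The first step is 0.05/4 = 0.0125. Same power function and SDs:

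| Scale | n = 75, 0.05 → 0.0125 | n = 100, 0.05 → 0.0125 | Predicted change |
|---|---|---|---|
| 0-10 | 0.82 → 0.99 | 0.71 → 0.85 | 2-3 |
| 0-3 | 0.25 → 0.30 | 0.21 → 0.25 | 1-2 |

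**The case against.** The strongest reply is that Section G predicts a fall on each of the four scales. If support means that all four fall, the false-claim rate is below that of a single test. This shows that the plan's silence does not always inflate error. But the plan offers this as a prediction and nowhere makes it the condition for success.

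A reader might go further than the documents allow in three ways.

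- **Counting all 36 contrasts (6 outcomes × 6 pairs).** Without gating, this gives 57-75% for a false result in either direction (correlation 0.7 down to 0). Section G speaks of contrasts of interest, not all contrasts. The power statement frames the comparison as before against after, and the scalp measures are expected to stay stable. That figure should not set the weight of this point.
- **Saying that no test addresses A2.** The plan does state a mixed-model time test and contrasts for each component, with predicted direction and size. What is missing is the rule that combines them.
- **Concluding that the study is invalid.** A barely significant change would be about 0.5-0.6 points on a 0-10 scale (at n = 75, 1.99 × 2.5/8.660 = 0.575), well short of the predicted 2-3. Readers could see that it falls short.

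It is also fair to say that the larger uncertainty is the lack of a control group, which no multiplicity rule addresses. That stands.

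**Conclusion.** The point holds in a limited form. Section G applies an unadjusted 0.05 to each test, names no primary visit, and does not say what pattern of results answers A2. If any significant fall on the four scales counts, the chance of a false improvement is about 5-10% at a single visit and about 11-23% over all twelve ungated month-0 contrasts, against 2.5% for one test. It is 2-4% if only month 12 v 0 is tested after a significant time test, and under 1% if all four scales must fall.

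The rates illustrate the readings that the plan leaves open. They assume between-outcome correlations from 0 to 0.9, no dropout, and simpler tests in place of the planned mixed model. The change is worth making because it is cheap and the rule as written permits the inflated readings. It would not show that any improvement is due to the drug.

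**What to change.** In Section G, name one follow-up visit to compare with month 0, and test the four symptom and sign scales there with Holm adjustment (first step 0.0125). In the simulations this holds the chance of any false claim, in either direction, at 2.6-4.9%. An alternative is one named primary scale at 0.05, with Holm over the other three (first step 0.05/3 = 0.0167) only if it is significant. Holm over all four sits closer to C1, which lists symptoms and signs together. Adjust the wording of A2 and C1 to match.

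Report the remaining contrasts and the two scalp measures as estimates with 95% confidence intervals and no significance claims. The plan expects the scalp measures to stay stable, and a non-significant test would not show that.

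**Cost.** No extra patients, visits or data. Detectable differences rise as shown in step 4 but stay well below the predicted changes. Even at 0.05/36 = 0.0014, power for the smallest predicted changes (2 points and 1 point) exceeds 99.9% at n = 75 under the assumed SDs. The real downside is that scalp involvement gets no formal test, although A2 names disease progression.

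**Before naming the visit.** The abstract (A1) says "Patients would be seen at monthly intervals over a period of six months to monitor their progress", while 3.e, F2 and G use months 0, 3, 6 and 12. These sections must be reconciled first. That contradiction is a separate issue and not evidence for this one.
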